## 1. Title of Study

A prospective, made in public and randomly allocated clinical study for a single-arm in a single-center to assess the preciseness of a wrist band type blood pressure gauge, H2-BP for measuring the blood pressure on radial artery.

## 2. Summary of the protocol

Objectives of Study	Compare and assess the accuracy of wrist band type and stethoscope type blood pressure gauge by applying to the out subjects, hospitalized patients and applicants who show symptoms of hypotension, normal blood pressure, borderline hypertension and high blood pressure
Overview of Study Design	Prospective, single-arm, single-center, open-label, non-randomized study
Clinical Trial Institution	Gangnam Severance Hospital, Yonsei university
Count of targeted subjects	
141subjects (Minimum 85 subjects)
 
The subjects of this study should be recruited while taking the following into account
 
1. Wrist Circumference Distribution of Study Subjects
 

At least 20% of the experimenters shall have the circumference within 1/4 of the entire limb circumference. (Minimum 17 subjects)

At least 10% of the experimenters shall have the circumference within top 1/8 of the entire limb circumference. (Minimum 9 subjects)

At least 10% of the experimenters shall have the circumference within lowest 1/8 of the entire limb circumference. (Minimum 9 subjects)

 
H2-BP shall take the wrist circumference as the criterion of measuring as it is a wrist band type and measures the pressure by wearing on the wrist. The wrist circumference is marked in centimeter. The minimum subjects in each sector are as follows as H2-BP is regulated for the people with 15-19cm wrist circumference to use the unit.
 

15.0–15.5625 cm: At least 10% (minimum 9 subjects)

15.5625–16.125 cm: At least 10% (minimum 9 subjects)

16.125–17.25 cm: At least 20% (minimum 17 subjects)

17.25–18.375 cm: At least 20% (minimum 17 subjects)

18.375–18.9375 cm: At least 10% (minimum 9 subjects)

18.9375–19.5 cm: At least 10% (minimum 9 subjects)

 
2. Age Constitution
 
- Over 19

	
3. Gender Constitution of Study subjects
 

- Minimum respective 30% of female and male shall constitute entire subjects

 
4. Upper Arm Circumference Distribution of Study Subjects
 

- The bladder length of the comparator device should be 75–100% of the subject's upper arm circumference.

- The bladder width of the comparator device should be 37–50% of the subject's upper arm circumference.

Inclusion/Exclusion Criteria	
1. Inclusion/Exclusion Criteria for Subjects of the Investigational Device
 
1) Inclusion Criteria
 

(1) The out patients, hospitalized patients and applicants over 19 who show symptoms of hypotension, normal blood pressure, borderline hypertension and high blood pressure

(2) Inclusion of patients who meet the count of the targeted patient and rationale of estimation, i.e. wrist circumference, age, gender and circumference of the upper arm (Refer to section 6)

(3) Inclusion of patients who agreed in written form to decide the participation and comply the cautions after listening and understanding fully the details on this clinical study.

 
2) Exclusion Criteria
 

(1) The subjects who disagreed to participate into this study

(2) The subjects likely not to maintain the constant blood pressure about 30 minutes due to hypovolemia or quasi equivalent disease and situation

(3) The subjects likely not to maintain the constant blood pressure about 30 minutes due to short-termly active vasoactive agonist or quasi equivalent medication

(4) Subjects with cardiac arrhythmia

(5) Subjects who ate food within 30 minutes

(6) The patients who took caffeine drink within 1 hour or smoked within 15 minutes

(7) The subjects who made exercise immediately before measuring the blood pressure

(8) Other subjects who are inappropriate to this study by the decision of the research staff

	
2. Inclusion/Exclusion Criteria for Users of the Investigational Device
 
1) Inclusion Criteria
 
(1) The subjects to be tested with the stethoscope type blood pressure gauge shall acquire appropriate hearing power and eyesight.
 
(2) The subjects to be tested with the stethoscope type blood pressure gauge shall have training and experience on measuring.
 
(3) The subjects who voluntarily agreed to sign after listening the explanation on the objective and procedure of the clinical study
 
2) Exclusion Criteria
 
The subjects who were decided as inappropriate for participating into the clinical study by the person in charge for the clinical study and other research staff

Clinical study Period	About 23 months - Study Protocol and IRB Approval: approximately 2 months - Study Contract and Administrative Procedures Execution: approximately 1month - Subject Recruitment and Study Procedure Execution: approximately 19 months - Analyze data and report results: approximately 1 month
Investigational Device	
1. Investigational Device
 
1) Model: H2-BP 2) Product name(Product category No.) and class: Automatic electronic blood pressure gauge(A23010.04)/Class II 3) Manufacturer: Charmcare Co., Ltd 4) Shape and structure: -H: 81.5mm, L: 79.5mm, W: 25.5mm 5) Storage conditions: Store at room temperature
 
2. Comparator
 
1) Model: big ben® Sphygmomanometer 2) Product name(Product category No.) and class: Aneroid type blood pressure gauge(A23010.01) / class I 3) Manufacturer: Riester 4) Shape and structure: - H: 250mm, L: 250mm, W: 250mm 5) Storage conditions: Store at room temperature

Instructions for use	The Investigational Device will be applied to one wrist of the patient to measure blood pressure, followed by the application of the comparator to the upper arm of the same arm to measure blood pressure. The procedure for use

	
is as follows.
 
1. Investigational Device (H2-BP)
 
The device is applied to the subject's wrist, and pressure inflation begins when the button is pressed. Once the measurement is complete, the systolic and diastolic blood pressure values are displayed on the screen. For detailed instructions on usage, refer to Appendix 2_H2-BP User Manual0-42_Full Document.
 
2. Comparator (big ben® Sphygmomanometer)
 
After placing the cuff around the upper arm, the pump is manually pressed to inflate the cuff. Two operator each using a separate stethoscope connected to the same cuff, independently measure the systolic and diastolic blood pressure.

Test method	
This clinical study is a prospective, single-arm, single-center, open-label, non-randomized study conducted over one day. After providing a thorough explanation of the study, informed consent is voluntarily obtained in writing from outpatients, inpatients, and subjects aged 19 years or older with hypotension, normotension, borderline hypertension, or hypertension.
 
Each subject is assigned a screening number, and eligibility (inclusion/exclusion) criteria are assessed. Demographic information (date of birth, age, and gender) is collected, and the use of prior or concomitant medications is reviewed. The wrist and upper arm circumference of the subjects are measured, and those deemed eligible are enrolled in the clinical study.
 
1. test method
 
The wrist band-type blood pressure monitor H2-BP and the auscultatory blood pressure measurement device are used to measure blood pressure on the same arm. The wrist band-type blood pressure monitor is operated by a single operator who records the measurement values, while the auscultatory blood pressure device is used by two independent operators who measure blood pressure simultaneously.
 
For each subject, the H2-BP is worn on one wrist, and the auscultatory blood pressure device is applied alternately to the upper arm of the same arm. Measurements are repeated until three valid pairs of measurements are obtained from a single subject, with a maximum of eight measurement attempts allowed per subject.
 
2. reading criteria

	
The two operators performing auscultatory blood pressure measurements must measure blood pressure independently for each subject, ensuring that they are blinded to each other's readings. Additionally, the operators must not have access to the measurement values displayed by the investigational device during the procedure.
 
For each subject, measurements are repeated for 10 to 30 minutes until three valid blood pressure readings are obtained. All recorded values are documented accordingly.

Endpoint	
-Primary Endpoint : Average on difference between blood pressures measured with test device and reference device, Standard deviation on the blood pressures measured with test device and reference device. (Based on count of measurement)
 
-Secondary Endpoint : Standard deviation on difference between blood pressures measured with test device and reference device. (Based on the count of the patients)

Visit schedule	
2 days in total : Screening(Visit 1), Medical instrument application(Visit 2)
 
If the screening process does not take a significant amount of time, both screening and medical device application may be conducted during Visit 1.

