## 9. Study Design and Methodology

This clinical study is a single-arm, single-center, open-label, non-randomized, prospective, single-day study. The investigational device will be applied for blood pressure measurement in outpatients, inpatients, and volunteers aged 19 years or older who present with hypotension, normotension, borderline hypertension, or hypertension.

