### 9.1 Implementation of Monitoring for Subjects Using the Investigational Device

For subjects undergoing monitoring (or their legally authorized representatives, if applicable), screening shall be conducted after obtaining written informed consent for participation in the clinical study. Based on the screening assessment, subjects who meet the inclusion criteria and do not meet the exclusion criteria will be enrolled in the study.

Blood pressure measurements will be performed in a seated position, alternating between the investigational device and the comparator device. The measurement procedure follows the steps below:

1. Using the comparator device, one valid pair of systolic and diastolic blood pressure (BP) values will be obtained from the upper arm as shown in Figure 1.
2. The investigational device will then be applied to the same arm's wrist, and one valid pair of systolic and diastolic BP values will be obtained.
3. Steps 1 and 2 will be repeated until three valid pairs of BP values are collected for each subject. A minimum interval of 60 seconds will be maintained between each measurement.
4. The same procedure will be followed for all other enrolled subjects.

[figure not shown]

Figure 1. ①Stethoscope ②Comparator Device Manometer ③Pump ④Investigational Device

The investigational device measurement is recorded by a single operator. In contrast, the comparator device measurement is recorded by two independent operators, each using a separate stethoscope to simultaneously assess and document the blood pressure readings.

When measuring diastolic blood pressure (DBP) using auscultation, Korotkoff Phase V should be recorded. If Korotkoff Phase V is not audible, the subject shall be excluded from the study.

The two operators using the auscultatory blood pressure measurement method must conduct their measurements independently, ensuring that they cannot communicate or be aware of each other's recorded values for each subject. Additionally, during the measurement process, the operators must not have access to the investigational device's readings.

\* If the difference between the two simultaneous measurements exceeds the following thresholds, the corresponding blood pressure value pair shall be excluded:

- If the systolic blood pressure (SBP) difference between the two operators is greater than 4 mmHg, the value pair is excluded.

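### The H2-BP operator is not masked to the comparator and a valid H2-BP reading is not defined, so selective repetition that could lower the standard-deviation endpoints is not prevented

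*Combined protocol and SAP*

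**What the plan says.** **Repetition.** Section 2 (Test method) states: "Measurements are repeated until three valid pairs of measurements are obtained from a single subject, with a maximum of eight measurement attempts" allowed per subject. Section 9.1 has the same stopping rule without a cap: "Steps 1 and 2 will be repeated until three valid pairs of BP values are collected for each subject".

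**Validity.** Section 9.1 uses the word *valid* for the pair from each device. The criteria it gives are for auscultation only. One is "If the systolic blood pressure (SBP) difference between the two operators is greater than 4 mmHg, the value pair is excluded", with the same rule for diastolic pressure. The other is that Korotkoff Phase V must be audible. The stability rule in Section 13 (1.60 kPa systolic, 1.07 kPa diastolic) also concerns the reference device, and the outlier rule in Section 15.1(d) refers back to the exclusion and dropout criteria.

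**Masking.** The two auscultators are kept from each other's values, and Section 2 adds that "the operators must not have access to the measurement values displayed by the investigational device during the procedure". For the other side, Section 9.1 says only: "The investigational device measurement is recorded by a single operator". Section 9 calls the trial a "single-arm, single-center, open-label, non-randomized, prospective, single-day study".

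**Order.** Section 9.1 takes the comparator first. The instructions for use in Section 2 put H2-BP first.

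**Acceptance.** Section 11.1 limits the mean difference to ±0.67 kPa and s_n to below 1.07 kPa. Section 11.2 judges s_m against Table 1 or 2.

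**The concern.** The session runs until three valid pairs exist, so someone decides on the spot whether each attempt counts. For the comparator that decision has a numerical rule. For H2-BP it has none, and the person who takes and records the reading may know the auscultatory value. A reading that looks wrong can be repeated in good faith, and the readings that look wrong are those far from the reference.

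The acceptance statistics are standard deviations of exactly these differences. Removing the large ones lowers s_n and s_m directly, and no later analysis can restore readings that never entered the data set. A low SD would then be hard to tell apart from selective repetition.

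**Working it through.** **Plan figures.** 85 subjects × 3 readings = 255, as stated in Section 11. With 1 kPa = 7.50062 mmHg, the s_n limit is 1.07 × 7.50062 = 8.03 mmHg and the mean limit is 0.67 × 7.50062 = 5.03 mmHg. Table 1 gives an s_m limit of 6.95 mmHg at mean 0. The documents give no figure for the effect of selection, so the rest rests on assumptions.

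**Model 1 (assumed).** Difference = subject effect N(0, 6) + reading error N(0, 7), in mmHg; up to eight attempts; the first three accepted readings are kept.

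Without selection:
- s_n = √(6² + 7²) = √85 = 9.2
- s_m = √(6² + 7²/3) = √52.3 = 7.2

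Both fail. At a 15 mmHg cut-off the share of readings rejected is 2 × [1 − Φ(15/9.22)] = 10.4%. Simulated results:

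| H2-BP readings rejected | s_n (limit 8.03) | s_m (limit 6.95) |
|---|---|---|
| none | 9.2 | 7.2 |
| all beyond 20 mmHg | 8.5 | 6.6 |
| all beyond 18 mmHg | 8.1 | 6.2 |
| half of those beyond 15 mmHg | 8.5 | 6.5 |
| half of those beyond 12 mmHg | 8.2 | 6.3 |
| all beyond 15 mmHg | 7.3 | 5.5 |
| all beyond 12 mmHg | 6.2 | 4.5 |

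At the 15 mmHg cut-off about 99% of subjects still complete, using 3.4 attempts on average, so the selection would not show up as lost subjects. These are long-run values. In single trials of 85 subjects the chance of meeting the s_n limit is under 1% without selection, 11% to 12% at 20 mmHg, 41% to 42% at 18 mmHg and 99.7% at 15 mmHg.

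**Model 2 (assumed).** This follows the plan more closely: comparator readings alternate with H2-BP, the reference is the mean of the readings before and after as in Section 11.1, and the comparator fluctuates with SD 3 mmHg. A device reading is rejected if it is too far from the preceding comparator reading. There are 85 subjects and the true SD of the difference is 9 mmHg.
- Within-subject correlation 0.5, no rejection: s_n 8.97, s_m 7.40, s_n limit met in 2.5% of trials.
- All beyond 15 mmHg rejected, eight attempts: s_n 7.44, s_m 5.94, limit met in 94%.
- Same cut-off, correlation 0.3 and 0.7: limit met in 99.8% and 63%.
- Same cut-off, correlation 0.5, only one spare attempt: s_n 8.02, limit met in 52%.

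The last case matters because Section 2 does not say whether an attempt is a pair or a single reading. The direction was the same in every setting tried; the size depends on the inputs.

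**The case against.** Three stronger readings are tempting, and the documents do not support them.

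First, a reader might infer that the H2-BP operator must see both auscultatory values, because someone has to apply the 4 mmHg rule and the auscultators may not. The protocol describes other people: the investigator (Sections 6 and 10.2), the device manager (Section 8) and designated research personnel (Section 18.1). It does not say who applies the rule. What stands is that no masking of the device operator is stated.

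Second, a reader might infer that the plan permits discarding discordant H2-BP readings. It does not. Every value-based exclusion concerns the comparator, recorded values are to be documented, and Section 20 provides for source and case report form checks every three months. The natural meaning of a valid device reading is one that the device displays. The user manual (Appendix 2), not among the documents reviewed, may define error readings. What stands is that the protocol states no such criterion, bars no rejection by value, and does not say which readings are analysed when more than three exist.

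Third, a reader might infer that a failing device would pass. In Model 1 the average s_n falls below its limit only with near-systematic rejection at about 15 mmHg or tighter. The secondary limit is crossed sooner, because s_m starts closer to it.

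The conflicting order in Section 2 means that a comparator value may not precede the first H2-BP reading. Since readings alternate, this weakens the argument for that reading only.

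**Conclusion.** The concern holds as a gap in protection. It is not evidence that selection will occur, and no misconduct is implied. Masking runs one way, device validity has no criterion, and the stopping rule allows repeats, so rejection on the device value is not prevented and could reduce s_n and s_m. The mean limit applies as well, so the SDs are not the only deciding quantities.

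The size is conditional. Under SDs of 6 and 7 mmHg and zero mean difference, complete rejection beyond 15 mmHg moves s_n from failing to passing; cut-offs of 18 to 20 mmHg, or half rejection at 15 mmHg, do not on average. None of the SDs, correlations, cut-offs or rejection rates comes from the documents. The change should be made because it is cheap and cannot be made after the readings are taken.

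**What to change.** Amend Sections 2 and 9.1 as follows.

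- **Validity.** An H2-BP reading is valid whenever systolic and diastolic values are displayed without a device error, and may not be rejected for its value.
- **Analysed readings.** Analyse the first three device readings in time order whose comparator readings before and after (i and i+1 in Section 11.1) both meet the 4 mmHg rule.
- **Masking.** The device operator records the displayed value before learning any comparator value. An existing team member, other than that operator and the two auscultators, applies the 4 mmHg check and announces only *repeat* or *continue*.
- **Record.** Log every attempt with the reason for any invalidity, and report the number of rejected device readings.
- **Consistency.** Reconcile the measurement order and the attempt cap between Sections 2 and 9.1.

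The cost is protocol wording, an attempt log on the case report form, and assigning a team member to the check. s_n and s_m may be slightly less favourable because motion-affected readings stay in.

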### 3. Research Background and Theoretical Basis

The cardio pulmonary diseases from hypertension, arteriosclerosis and cerebral apoplexy emerge one of the factors threatening the modernists' health. According to the report from Statistics Korea in 2022, cardio pulmonary diseases ranked 2nd and 3rd in cause of death in Korea. According to the report from Statistics Korea in 2022, cardio pulmonary diseases ranked 2nd and 3rd in cause of death in Korea. Over 610K people per annum in USA died for cardiac diseases. The blood pressure control is one of the important factors in monitoring such cardiac pulmonary diseases. The blood pressure is controlled by monitoring always with blood pressure measuring tool.

The crucial point in blood pressure measuring is the preciseness. Inaccurately measured blood pressure not only reach to its inaccuracy but also can make bad influence on the health of normal patients and hypertension patients as well by resulting in unnecessary treatment and improper control. Accordingly, the righteous understanding on how to measure and how to manage the gauge lead to measure the blood pressure exactly. Moreover, measuring the blood pressure 1-2 times can be short for exact diagnosis and treatment as it fluctuates daily and changes every time every minute depending on the activities of the patients. The electronic blood pressure gauge has a merit for heightening the reliability in blood pressure data as a few times checking are easier.

Lk++

The H2-BP from Charmcare is a blood pressure gauge to measure the blood pressure at systolic and diastolic area of the adults non-invasively. It is configured with main body, cuff, band and charging cable. Repeated pressing on the measuring button pressurizes the cuff automatically and measures the highest and lowest blood pressure and pulse by using oscillometric. H2-BP is used by wearing on the wrist like a usual wrist watch. The convenience in using by the patient is improved and it provides the environment for more frequent monitoring. Therefore, the clinical test for the accuracy of H2-BP will be made by comparing the data measured by H2-BP and stethoscope type blood pressure gauge.

#### **4. Objectives of Study**

This study is purposed to compare and assess the accuracy of wrist band type and stethoscope type blood pressure gauge by applying to the out patients, hospitalized patients and applicants who show symptoms of hypotension, normal blood pressure, borderline hypertension and high blood pressure.

#### **5. Risk/Benefit Analysis**

##### **5.1 Risks of participating in research**

In this study, subjects will have their blood pressure measured using standard methods and will additionally have their blood pressure measured using the H2-BP wrist band blood pressure monitor. Blood pressure measurement is a non-invasive test and poses little additional risk to subjects from participating in the study.

##### **5.2 Benefits of participating in research**

While there is no direct benefit to you as a participant in this clinical study, you may benefit from the results of this study, which will help validate the accuracy of wearable blood pressure monitors for convenient blood pressure measurement and provide information about more convenient and useful products for people with related conditions.

##### **5.3 Risk/Benefit Analysis**

There is no additional risk of harm from this study, and the benefits to society outweigh the anticipated inconvenience of the research.

## 6. Planned Sample Size

Planned Sample Size: 141 Subjects (Minimum Enrollment: 85 Subjects)

Rationale for Sample Size Calculation: According to the guidelines outlined in ISO 81060-2 Third Edition 2018-11 (Non-invasive sphygmomanometers - Part 2: Clinical investigation of intermittent automated measurement type [including: Amendment 1 (2020)]) and EN 1060-4 (Non-invasive sphygmomanometers - Part 4: Test procedures to determine the overall system accuracy of automated non-invasive sphygmomanometers), a minimum of 85 subjects must be enrolled to evaluate the accuracy of electronic sphygmomanometers.

Considering potential data loss due to withdrawal of consent and other unforeseen circumstances, an anticipated dropout rate of approximately 40% has been applied. Accordingly, a total of 141 subjects will be recruited for this study.

Composition of Study Subjects: In accordance with the ISO 81060-2 Third Edition 2018-11 international standard for the clinical validation of electronic sphygmomanometers, the enrolled subjects must meet the following composition criteria.

The investigator is responsible for continuous monitoring of subject enrollment status to ensure compliance with the required composition. If the composition criteria are not met, additional subjects may be recruited as necessary to fulfill the requirements.

